9.2 Efficacy Assessments

9.2.1 Clinician-rated Scales

9.2.1.1 Use of Clinician-rated Scales

The following assessment tools will be used:

- CDRS-R – assessing depressive symptoms
- CGI – assessing global impression
- CGAS – assessing functionality

Detailed instructions on how to administer the scales and how to score using the scales will be provided to the site in a *Rater Station Site Manual*.

The CDRS-R and CGAS will be administered in the local language. Only scales provided by Lundbeck that have been validated in the language to which they have been translated will be used in this study. The CGI will be administered in English.

9.2.1.2 Children Depression Rating Scale Revised Version (CDRS-R)

The CDRS-R²² is a clinician-rated scale to measure the severity of depression of children and adolescents. The CDRS-R consists of 17 items: 14 items rate verbal observations, and three items rate nonverbal observations (tempo of language, hypoactivity, and nonverbal expression of depressed affect). Depression symptoms are rated on a 5-point scale from 1 to 5 for the verbal observations, and a 7-point scale from 1 to 7 for the nonverbal observations. The total score ranges from 17 (normal) to 113 (severe depression). The CDRS-R can be administered by a clinician after a training session. It takes approximately 20 to 30 minutes to administer and rate the CDRS-R.

9.2.1.3 Clinical Global Impression scales (CGI-S/I)

The CGI²³ was developed to provide global measures of the severity of a patient's clinical condition and improvement or worsening during clinical studies.

The clinician will use the scale to assess depressive symptoms.

The CGI consists of two clinician-rated subscales: severity of illness (CGI-S) and global improvement (CGI-I).

The CGI-S provides the clinician's impression of the patient's current state of mental illness. The clinician uses his or her clinical experience of this patient population to rate the severity of the patient's current mental illness on a 7-point scale ranging from 1 (*Normal - not at all ill*) to 7 (*among the most extremely ill patients*).

The CGI-I provides the clinician's impression of the patient's improvement (or worsening) from Baseline A in the lead-in studies. The clinician assesses the patient's condition relative to a baseline on a 7-point scale ranging from 1 (*very much improved*) to 7 (*very much worse*). In all cases, the assessment should be made independent of whether the rater believes the improvement is drug-related or not.

An experienced clinician can use the CGI after a short training session. It takes 1 to 2 minutes to score the CGI after a clinical interview.

9.2.1.4 Children's Global Assessment Scale (CGAS)

The CGAS²⁹ is a clinician-rated global scale to measure the lowest level of functioning for a child (4 to 16 years) during a specified time period. The CGAS contains behaviourally-oriented descriptors at each anchor point that depict behaviours and life situations applicable to a child. The items range in value from 1 (most functionally impaired child) to 100 (the healthiest). A total score above 70 indicates normal function. The CGAS can be administered by a clinician after a training session. It takes approximately 2 minutes to administer CGAS.

9.2.1.5 CDRS-R, CGI, CGAS Rater Qualification and Certification

The CDRS-R, CGI and CGAS scales should only be administered by a rater who has adequate experience with paediatric patients with MDD and who has adequate experience in rating scales. The rater should be a psychiatrist or DO specialised in child and adolescent psychiatry, or a clinical paediatric (neuro-) psychologist involved in clinical practice.

The CGI should be administered by the investigator responsible for the patient. The investigator must be psychiatrists or DO specialised in child and adolescent psychiatry that has adequate experience with paediatric patients with MDD.

Any exceptions must be discussed and approved by Lundbeck.

Only raters who have been already trained and certified in Study 12709A or Study 12710A are allowed to rate the patients in Study 12712A. The certificate(s) issued during Study 12709A or Study 12710A cover the extension study and no additional certificate will be issued.

New raters joining Study 12712A will be trained and certified using the same certification processes as in Study 12709A and Study 12710A. Documentation of training and certification will be delivered to the raters for arching in the investigator trial master file (TMF). No patient may be rated before the documentation has been delivered.

For each individual patient, the same certified rater should rate the patient, and preferably the same as in Study 12709A or Study 12710A study. For unforeseen circumstances, certified back-up raters should be available throughout the study.

9.2.2 Patient and/or Parent Reported Outcomes (PROs)

9.2.2.1 Use of PROs

The following PRO will be used:

- BRIEF – Assessing cognitive function
- PedsQL VAS – assessing functionality

9.2.2.1.1 Behavioural Rating Inventory of Executive Function® (BRIEF®)

The BRIEF³⁰ is a patient and carer-rated scale designed to measure executive function behaviour in children and adolescents in an everyday environment. We use BRIEF (parent form) for the children aged 7 to 11 years and BRIEF-SR (self-report) for the adolescents aged 12 to 18 years. Both versions of the BRIEF contain 86 items. Items are rated on a 3-point scale, from N (never) to O (often). These items cover 8 non-overlapping clinical scales: 3 scales in the Behavioural Regulation Index (inhibit, shift and emotional control), and 5 scales in the Metacognition Index (initiate, working memory, plan/organize, organisation of materials, and monitor). The clinical scales also provide the Global Executive Composite score, which represents the child's overall executive function behaviour. There are 2 validity scales: negativity and inconsistency. It takes approximately 30 minutes to complete and score the BRIEF.

9.2.2.1.2 PedsQL Present Functioning Visual Analogue Scales (PedsQL™ VAS)

The PedsQL™ VAS³¹ is designed to measure at-that-moment functioning in children and adolescents. The PedsQL VAS consists of 6 domains: anxiety, sadness, anger, worry, fatigue and pain using visual analogue scales. The functionality for each domain is measured on a 10 cm line with a happy face at one end and a sad face at the other. The patients are asked to mark on the line how they feel. The total score is the average of all 6 items, and the emotional distress summary score is the mean of the anxiety, sadness, anger, and worry items. It takes 2 to 5 minutes to administer and rate the PedsQL VAS.

9.3 Blood Sampling for Vortioxetine Quantification

Blood samples (2 x 1 mL) for IMP analysis will be collected in EDTA tubes simultaneously with clinical safety lab samples. The blood sampling and handling procedures are described in the study-specific *Laboratory Specification Manual*.

The blood samples will be analysed for vortioxetine using a method validated in accordance with the EMA *Guideline on Bioanalytical Method Validation*³² and the FDA *Guidance for Industry*.³³ A bioanalytical protocol will be prepared by Lundbeck before the plasma samples are analysed.

The results of the bioassay will be given will be given in the bioanalytical study report that will be prepared by the Department of Bioanalysis, H. Lundbeck A/S.

9.4 Safety Assessments

9.4.1 Adverse Events

The patients will be asked a non-leading question (for example, “how do you feel?”, “how have you felt since your last visit?”) at each visit, starting at the Baseline Extension A Visit. Adverse events (including worsening of concurrent disorders, new disorders, and pregnancies) either observed by the investigator or reported spontaneously by the patient will be recorded, and the investigator will assess the seriousness and the intensity of the adverse event and its relationship to the IMP. Results from relevant tests and examinations, such as clinical safety laboratory tests, vital signs, and ECGs, or their corresponding conditions will also be recorded as adverse events if considered by the investigator to be clinically significant.

See chapter [10](#) for further information on adverse events.

9.4.2 Clinical Safety Laboratory Tests

The clinical safety laboratory tests are listed in [Panel 4](#).

Results of safety laboratory tests for Visit 12 (Completion Visit) of the lead-in studies 12709A or 12710A will be transcribed to Visit 1 (Baseline Extension A) of 12712A study (i.e. these tests should not be collected at Visit 1). However, the Hormones laboratory tests are specific for the 12712A study and will be collected at the 12712A Visit 1 using a separate kit.

Panel 4 Clinical Safety Laboratory Tests

Haematology B-haemoglobin B-erythrocyte count B-haematocrit B-total leucocyte count B-neutrophils (% of total leucocytes) B-eosinophils (% of total leucocytes) B-basophils (% of total leucocytes) B-lymphocytes (% of total leucocytes) B-monocytes (% of total leucocytes) B-thrombocyte count	Electrolytes^a S-sodium S-potassium S-calcium (total)	Urine^b U-protein (dipstick) U-glucose (dipstick) U-blood (dipstick) U-ketones (dipstick)	
		Endocrine and Metabolic^a S-albumin S-glucose (non fasting)	
		Kidney^a S-creatinine S-urea nitrogen (BUN)	
	Hormones S-estradiol (girls) S-total testosterone (boys) S-LH S-FSH S-LHRH S-prolactin S-TSH ^c	Urine Drug Screen^e U-amphetamines (incl. methamphetamine) U-barbiturates U-benzodiazepines U-cannabinoids U-cocaine U-opiates U-phenocyclidine	
		Blood Alcohol Screen^e B-ethanol	
		Infection S-C-reactive protein (CRP)	
	Serology^c B-HBsAg B-anti HCV		
B – blood; P – plasma; S – serum; U – urine			

 a. Clinical chemistry b. Microscopic examination (leucocytes, erythrocytes, and casts) will be performed only if any of the urine evaluations are abnormal. c. TSH and hepatitis B and C panels are optional and may be performed at the investigator's discretion if there is clinical justification. d. Females >10 years of age or female patients at lower age judged by the investigator to be of childbearing potential. Additional pregnancy tests during the study will be performed according to local requirements. Females under 11 years will be tested with a urine hCG test and females over 11 years will be tested with using a blood hCG test. e. It is not mandatory to screen for drugs and/or alcohol. However, it can be performed at any visit, at the discretion of the investigator. 			

Blood samples for the clinical safety laboratory tests will be collected as outlined in [Panel 2](#). The blood sampling and handling procedures are described in the study-specific *Laboratory Specification Manual*.

The blood and urine drug screen samples will be analysed at the central laboratory.

The additional urine samples will be collected and analysed at the site using dipsticks. If the dipstick evaluation is positive or abnormal, further analysis will be performed at the central laboratory.

The investigator must review (initial and date) the results of the clinical safety laboratory tests as soon as possible after receipt of those results. Out-of-range values must be interpreted by the investigator as “not clinically significant” or “clinically significant” with a comment concerning the planned follow-up. Tests for clinically significant out-of-range values must be repeated, or an appropriate clinical follow-up must be arranged by the investigator and documented on the laboratory report, until the value has stabilised or until the value has returned to a clinically acceptable value (regardless of relationship to IMP). Any value that is out-of-range at the Completion or Withdrawal Visit and judged clinically significant must be followed according to accepted medical standards for up to 30 days or until the value normalises or stabilises or a diagnosis or reasonable explanation has been established. Any out-of-range values followed after the last protocol-specified contact with the patient will be documented in the patient’s medical record.

Clinically significant out-of-range values must be recorded as an adverse event on an *Adverse Event Form*.

The central laboratory will be notified by the sponsor when the biological samples may be destroyed.

9.4.3 Vital Signs

Blood pressure (BP) and pulse rate will be measured using a standard digital meter after the patient has rested for at least 5 minutes in a supine position.

The patient must then be instructed to change from a supine to a standing position in a manner that includes passing through a sitting position before assuming an upright position. Blood pressure and pulse rate will be measured after the patient has been standing for at least 1 minute but no longer than 5 minutes.

Vital signs should be assessed prior to blood sampling.

Abnormalities of clinical significance must be recorded as an adverse event on an *Adverse Event Form*.

9.4.4 Height and Weight

Height will be measured with a stadiometer, without shoes.

Patients will be weighed wearing light clothing and no shoes. A similar amount of clothing must be worn on each occasion.

Abnormalities of clinical significance must be recorded as an adverse event on an Adverse Event Form.

9.4.5 Menstrual Cycle

The following will be recorded:

- Age of menarche
- The length of the menstrual cycle (number of days from the first day of menstruation to the day before the first day of the next menstrual period)
- Menstrual cycle regularity

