9.6 Total Volume of Blood Drawn and Destruction of Biological Material

The volume of blood drawn from each patient will be approximately 13 ml at the required study visits.

Safety blood test drawn at the Visit 12 of the lead-in Study 12709A or 12710A will be used as the safety blood test for Baseline Extension A Visit (excluding the additional Hormones panel of approximately 5 ml). Hence, the total volume of the blood drawn for the entire study is approximately 31 ml.

Additional blood samples may be required if the original blood samples are not viable or if re-testing is required.

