## 12.2 General Methodology for Other Safety Data

Unless otherwise specified, tables, graphs, and listings will be based on the APTS, and the tables will be presented for all patients and by lead-in study and by lead-in treatment.

The denominators for the summaries of a given variable will be based on the number of patients with non-missing values at a given visit or during the assessment period.

Descriptive statistics for the safety variables, both absolute values and change from baselines (baseline at randomisation in lead-in study and OLEXA), will be presented by visit and for the last assessment. All available post-OLEXA assessments will be included in the identification of the last assessment.

The number and percentage of patients with at least one PCS value at any post-baseline assessment time point will be summarized by variable. All available assessments will be included in the evaluation of PCS values.

The number and percentage of patients with values out-of-reference range and/or PCS range will be summarized by variable, visit, and last post-baseline assessment.

For patients with post-baseline PCS values, listings will be provided including all the values for those patients for the variable, with flagging of PCS values and out-of-reference-range values.

The PCS definition will be provided by H. Lundbeck and are stated in [Appendix IV](#).

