## **Appendix II**

### **Study Flow Chart**

## Study Flow Chart

**Table 1 Study procedures and Assessments**

Visit	Base-line Extension A	Treatment Period												Completion /With-drawal a	Safety Follow-up b
Visit Number	1	2	3	4 c	5	6 c	7	8 c	9	10 c	11	12 c	13	14	
End of Week	0	1	2	3	4	6	8	10	12	15	18	22	26	30	
Visit Window d (days relative to nominal visit)	0 2	± 2	± 2	± 2	± 2	± 2	± 2	± 2	± 2	± 2	± 5	± 5	± 5	± 5	
Baseline Extension A Procedures and Assessments															
Signed informed consent/assent	✓														
Inclusion/exclusion criteria	✓														
Efficacy Assessments															
CDRS-R	✓ e	✓	✓		✓		✓		✓		✓		✓		
CGI-S	✓ e	✓	✓		✓		✓		✓		✓		✓		
CGI-I f	✓ e	✓	✓		✓		✓		✓		✓		✓		
BRIEF (7-11 years at Baseline Extension A)	✓				✓		✓		✓		✓		✓		
BRIEF-SR (12-18 years at Baseline Extension A)	✓				✓		✓		✓		✓		✓		
CGAS	✓ e				✓		✓		✓		✓		✓		
PedsQL VAS (PRO)	✓ e				✓		✓		✓		✓		✓		
Vortioxetine Quantification															
Blood sampling vortioxetine quantification	✓ e				✓								✓		
Safety Assessments															
Adverse events	✓ g	✓	✓	✓	✓	✓	✓	✓	✓	✓	✓	✓	✓	✓ h	
Blood and urine sampling for clinical safety laboratory tests	✓ e,i				✓								✓		
Vital signs	✓ e	✓	✓		✓		✓		✓		✓		✓		
Weight and height	✓ e								✓				✓		
Menstrual cycle and Tanner score	✓								✓				✓		
ECGs	✓ e				✓								✓		
Examinations	✓ e							✓					✓		

Visit	Base-line Extension A	Treatment Period												Completion /Withdrawal a	Safety Follow-up b
		2	3	4 c	5	6 c	7	8 c	9	10 c	11	12 c			
Visit Number	1	2	3	4 c	5	6 c	7	8 c	9	10 c	11	12 c	13	14	
End of Week	0	1	2	3	4	6	8	10	12	15	18	22	26	30	
Visit Window d (days relative to nominal visit)	0	± 2	± 2	± 2	± 2	± 2	± 2	± 2	± 2	± 2	± 5	± 5	± 5	± 5	
(physical and neurological)															
PAERS	✓ e	✓	✓	✓	✓	✓	✓	✓	✓	✓	✓	✓	✓		
C-SSRS	✓ e	✓	✓	✓	✓	✓	✓	✓	✓	✓	✓	✓	✓		
Other Study Procedures															
IMP dispensed	✓	✓	✓		✓		✓		✓		✓		✓		
Possible change in IMP dose		✓	✓		✓		✓		✓		✓		✓		
IMP returned and IMP accountability		✓	✓		✓		✓		✓		✓		✓		

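### Cycle day is not recorded at the hormone draws, so individual changes and out-of-range counts for estradiol, LH and FSH in menstruating girls cannot be separated from cycle phase; one date field would fix this

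*Protocol*

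**What the plan says.** - **Hormones.** Protocol 9.4.2, Panel 4, includes "Hormones S-estradiol (girls) S-total testosterone (boys) S-LH S-FSH S-LHRH S-prolactin" among the clinical safety laboratory tests. Values and changes of these tests are part of the primary endpoint (Protocol 16.1, SAP 3.1).
- **Baseline.** Protocol 9.4.2 says "the Hormones laboratory tests are specific for the 12712A study and will be collected at the 12712A Visit 1 using a separate kit". The hormone baseline is thus one new draw, with no lead-in hormone value behind it.
- **Sampling times.** In SAP Appendix II, Table 1, the row "Blood and urine sampling for clinical safety laboratory tests" is marked at Visits 1, 5 and 13. Nothing ties the draw to the cycle.
- **Menstrual data.** Protocol 9.4.5 lists three items: age of menarche, regularity, and a duration, "The length of the menstrual cycle (number of days from the first day of menstruation to the day before the first day of the next" period). Table 1 schedules them at Visits 1, 9 and 13 (Weeks 0, 12 and 26).
- **Analysis.** SAP 12.2 gives absolute values and change from OLEXA by visit and for the last assessment. It adds: "The number and percentage of patients with values out-of-reference range and/or PCS range will be summarized by variable, visit, and last post-baseline assessment". Cycle phase is not mentioned. SAP 12.6.4 summarises the menstrual items on their own, with no link to hormone results.

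**The concern.** A hormone that moves through the menstrual cycle gives a different value according to the day it is sampled. Cycle length and regularity do not place a sample within a cycle; for that one needs the date on which the last period began. At Week 4 blood is drawn but no menstrual item is collected at all.

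Two outputs suffer. An individual girl's rise or fall from OLEXA may be only a difference in sampling day. An out-of-range result may likewise be only a matter of timing if one range is used for the whole cycle. Anyone looking for an endocrine effect in post-menarcheal girls could not tell such values from a real change.

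**Working it through.** **1. The plan's own figure.** Protocol 9.6 gives about 13 ml at each required visit, with Visit 1 adding only the hormone panel ("excluding the additional Hormones panel of approximately 5 ml"), and a total of about 31 ml. With Visits 5 and 13 as the required visits, 2 × 13 + 5 = 31 ml. This reproduces the total and fits hormone draws at all three visits. It does not prove them, because the 13 ml is not broken down.

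**2. Chance of a different phase from Visit 1.** The documents give the nominal days, 4 × 7 = 28 and 26 × 7 = 182, and the visit windows, ±2 days at Week 4 and ±5 at Week 26. Assumptions: a 14-day luteal phase and a random cycle day at Visit 1.

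For a regular cycle of L days and a visit on day d, let s = d mod L. The share of girls in the other phase is 2 × min(s, L − s, 14, L − 14) / L.

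| Assumed cycle | Week 4 | Week 26 |
|---|---|---|
| 26 days, exact visit days | s = 2: 4/26 = 15% | s = 0: 0% |
| 28 days, exact visit days | s = 0: 0% | s = 14: 28/28 = 100% |
| 28 days, visits uniform over the windows | about 9% | about 80% |
| 30 days, exact visit days | 2 days short: 4/30 = 13% | s = 2: 4/30 = 13% |
| Mean 29, SD 3 days (simulated) | 17% | 49% |
| Same, plus SD 2 days within a girl | 20% | about 50% |
| Mean 29, SD 3, with windows | 19% | 49% |

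Over a spread of cycle lengths, Week 26 is close to random phase relative to Visit 1.

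**3. How much of an individual change is phase.** Assumed model: log hormone = the girl's level + a·cos(phase) + residual. Here a = ln(R)/2, R is the peak-to-trough ratio, and the residual variance is ln(1 + CV²). With independent phases at the two draws, the phase share of the variance of change is (a²/2) / (a²/2 + ln(1 + CV²)).

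Example, R = 3 and CV = 30%: a = 0.549, a²/2 = 0.151, ln(1.09) = 0.086, so the share is 0.151/0.237 = 64%.

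| R (assumed) | Share, CV 60% down to 20% |
|---|---|
| 1.5 | 6-34% |
| 2 | 16-60% |
| 3 | 33-79% |
| 5 | 51-89% |
| 8 | 64-93% |

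**4. Group mean change.** With random phase at Visit 1 the expected contribution of phase to the mean change is zero. For n girls, the 95% half-width is exp(1.96 × √(2(a²/2 + ln(1 + CV²))/n)) − 1. With an assumed 200 girls and CV 30% this is 8%, 10% and 13% for R = 2, 3 and 5. With no phase variation it would be exp(1.96 × √(2 × 0.086/200)) − 1 = 6%.

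**5. Out-of-range counts.** Suppose one fixed range covers a share q of cycle days. Phase alone then puts 1 − q of samples out of range, and 1 − q² of girls out at least once in two post-baseline samples with independent phases. For q = 95%, 85% and 75% this gives 5%, 15% and 25% of samples, and 10%, 28% and 44% of girls. The true q is unknown because the reference ranges are not in the documents.

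**The case against.** - **The planned outputs are mostly group summaries in a single-arm, descriptive study, and the primary objective rests on an overall clinical evaluation.** This stands. A reader might infer that phase biases the mean change or makes it worthless. It does not: with random phase at Visit 1 the mean is only less precise, and out-of-range percentages are inflated at OLEXA as well as later. The point concerns individual changes and flags.
- **The size is not known.** This stands. A reader might infer that these tables largely measure sampling day. The documents give no cyclic amplitude and no within-girl variation, and the computed share runs from 6% to 93%. Phase dominates only at roughly a 3-fold swing or more with moderate other variation.
- **Week 26 is not the opposite phase in general.** Since 182 = 6.5 × 28, a reader might infer that girls are sampled half a cycle out at Week 26. That needs an exact 28-day cycle and exact visit days. The windows lower it to about 80%, and a 26-day cycle is back in phase.
- **Protocol 17.10.2 promises further exploratory descriptions of variables that depend heavily on sex and age.** The list of examples is open, but phase is neither sex nor age, and no later table can recover a phase that was not recorded.
- **The gap may be covered elsewhere.** The Laboratory Specification Manual and the eCRF were not available. SAP Table 2 has no potentially clinically significant limits for these three hormones, and Protocol 9.4.2 has the investigator judge the significance of out-of-range values. So the gap is shown for the protocol and SAP only, and the flags at issue are reference-range flags. Phase-specific ranges would still need a recorded phase.

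**Conclusion.** The concern holds in a limited form. Neither document records cycle day or last-period date at the hormone draws, and Week 4 has no menstrual data. Individual changes from OLEXA and out-of-reference-range counts for estradiol, LH and FSH in menstruating girls therefore cannot be separated from cycle phase. Group means lose precision but are not biased if phase at Visit 1 is random.

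With cycles of mean 29 and SD 3 days and a 14-day luteal phase, about 17-20% of girls are in a different phase at Week 4 and about 50% at Week 26. These cycle figures are assumptions, as is the premise that the three hormones vary through the cycle. The documents do not state the number of menstruating girls. The point is a cheap improvement to a primary safety endpoint and does not call the study's overall safety evaluation into question.

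**What to change.** **Data.** Record the first day of the last menstrual period at Visits 1, 5 and 13, unless the laboratory manual or eCRF already captures it; in that case only the SAP needs to change.

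**SAP 12.2.** Keep the overall tables. Add estradiol, LH and FSH by menarcheal status, hormonal contraceptive use (contraceptives are allowed in Protocol Appendix II) and reported cycle phase at sampling. Use phase-specific reference ranges for the out-of-range counts where the laboratory has them. Give same-phase change from OLEXA as a supplementary table, not as the only one, because it would leave out about half of menstruating girls at Week 26 under the assumptions above.

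**If the date can no longer be collected.** Show pre-menarcheal girls separately, and state that individual changes and out-of-range counts in menstruating girls are not interpretable with respect to cycle phase.

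**Cost.** One date field at three existing draws and some extra table rows, with no extra blood. The downside is smaller cells, and phase is unreliable with irregular cycles or poorly recalled dates.
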